Protocol date: October 2018

SYNERGISTIC EFFECT OF EXCLUSIVE ENTERAL NUTRITION FORMULA IN ADDITION TO CORTICOSTEROIDS THERAPY TO INDUCE CLINICAL REMISSION IN PATIENTS WITH CROHN'S DISEASE: A PILOT STUDY INVOLVING A MULTIDIMENSIONAL ASSESSMENT OF POTENTIAL MECHANISMS

Principal Investigator: [name]

Co-PI: [name] MD;

Co-investigators: [name]; [name]; [name]; [name] MD; [name]; [name], NP; [name]; [name]; [name]; [name]; [name]; [name]; [name].

Student: [name]

Farncombe Family Digestive Health Research Institute- McMaster University

Lay Abstract

Crohn's disease (CD) is an inflammatory bowel disease (IBD) characterized by diarrhea, abdominal pain and bleeding. There are several treatment options but the most-widely used for acute therapy are corticosteroids (CS); unfortunately, CS are often associated with severe side effects. The administration of a formula for exclusive feeding (EEN) is well-established as an alternative to CS in children with Crohn's disease (CD). However, this intervention is not routinely used in adults, in part because of uncertainty regarding the magnitude of the benefit of EEN reported in previous studies. In fact, few studies have examined the effects of EEN in adult patients with active CD. We propose that a polymeric formula, provided orally, may help decrease gut inflammation and improve nutritional status through modulation of gut bacteria. We will therefore investigate the effect of exclusive formula feeding therapy in addition to different regimes of CS therapy compared to CS alone in adult patients with active CD, on symptoms and inflammation after 6 weeks of treatment. We will collect information through questionnaires that assess gut symptoms, quality of life, mood changes and dietary patterns. To investigate potential mechanisms, we will collect stool samples to characterize gut bacterial profiles, blood to determine inflammatory markers and evaluate gut movements (motility) before, and after the treatment. We hope that our results will lead to better understanding of the beneficial effect of exclusive formula feeding in addition to CS as a more efficacious alternative than CS alone, and to understand the mechanisms of this therapy.

BACKGROUND

Crohn's disease (CD) is characterized by inflammation of the gastrointestinal (GI) tract, diarrhea, pain and rectal bleeding¹. Canada has one of the highest prevalences of CD in the world with an estimated incidence rate of 16.3 per 100,000². The pathophysiology of CD is not well understood, but a dysregulated immune response to altered microbiota may play a key role³. Treatment of CD requires a multi-disciplinary approach involving medical therapy, surgery and dietary changes. Corticosteroids (CS) are the first line therapy to induce remission; however, they have adverse effects and 30% of patients can prove to be steroid resistant or dependent⁴. Therefore, alternative therapies that can effectively induce and maintain disease remission without short and long-term side effects are needed⁵.

Exclusive enteral therapy (EEN) involves a liquid diet of elemental or polymeric formula (PF), given exclusively over a prolonged period⁶. Elemental formula contains individual amino acids, while PF is providing intact proteins⁷. Although exclusive enteral nutrition (EEN) is used in children as an alternative to CS to induce remission due to its excellent safety profile⁷, it is not routinely used in adults.

The beneficial effects of EEN in CD were first demonstrated over two decades ago, when O'Morain et al⁸ demonstrated in a controlled study that an elemental diet was as effective as CS in achieving remission in adults with active CD. In particular, EEN was shown to induce the expression of growth factors, promote changes in intestinal permeability and stimulate mucosal healing^{8, 9}. Since then, several studies aimed to investigate this area. Meta-analyses of EEN versus CS have found that, although CS are superior to EEN in

inducing remission, EEN is also efficacious with expected remission rates of up to 60% and provides additional nutritional benefit^{5,10,20}. Although several studies have demonstrated effectiveness of elemental EEN in children, the effect of EEN in adult CD remain controversial^{5,7,20}.

Potential mechanisms by which EEN might act include relative bowel rest, reduced antigenic load, provision of trophic amino acids, local anti-inflammatory effects, and modification of gut microbiota^{11,20}. However, there is no strong evidence to fully support any one of these mechanisms. A recent meta-analysis²⁰ showed that the effects of the therapeutic formula on specific bacterial strains were variable and inconsistent among studies, possibly due to small sample sizes and methodological limitations. Our preliminary data showed that short term dietary changes improve motility in patients with low-grade gut inflammation²¹. However, the effects of EEN on gastrointestinal transit in adults has not been yet investigated.

Evidence for the effect of EEN on quality of life, an essential patient reported outcome, is particularly scarce. Guo *et al*³⁰ found an improvement of quality of life in 13 patients with CD receiving EEN for 6 weeks. However, it is currently unknown whether EEN is more effective than CS in improving quality of life in adults with CD.

The potentially synergistic effects of adding EEN to CS therapy have not been explored before. Therefore, we designed a randomized controlled trial with the objective to investigate the effect of EEN in addition to different regimes of CS therapy (ECS) compared to CS alone (CS), for decreasing disease activity and improving quality of life in adult patients with CD. We also propose to investigate potential mechanisms underlying any beneficial effect of EEN in CD in the context of concomitant CS therapy.

Hypotheses:

- 1- Six weeks of ECS will be more effective than CS in inducing clinical remission in patients with active CD
- 2- Six weeks of EEN in addition to a short course of CS (ECSC) will have similar efficacy than ECS and reduced number of adverse events
- 3- Six weeks of ECS will lead to beneficial changes in the composition and/or metabolic activity of the intestinal microbiota, gastrointestinal transit and inflammatory burden.

Because the effect size of ECS has not been investigated before, we will perform a pilot study to assess feasibility and calculate estimates of effect size in order to plan a larger trial. Based on the significant number of patients, if the study is feasible, we will consider the sample size estimated through this pilot study for the full trial to minimize the possibility of recruiting additional patients.

General aim and endpoint: To assess study feasibility and provide estimated effect sizes (point estimates with confidence intervals) for all measures of interest in order to plan an adequately powered study. We will assess recruitment rates and acceptability of treatment in arms involving exclusive enteral nutrition.

Primary outcome and endpoint: To assess the efficacy of 6 weeks of ECS in inducing remission (CDAI <150) compared to treatment with CS in adult patients with active CD (CDAI >220 and either CRP >5 or fecal calprotectin >250 mg/l).

Secondary outcomes and endpoints: To determine the beneficial effect of 6 weeks of ECS as compared to CS in inducing:

1. Clinical disease improvement (drop in CDAI >70 or 100)
2. Improvement in quality of life (using the Inflammatory Bowel Disease Questionnaire (increase IBDQ scores))
3. Biochemical remission (normalization of either serum CRP and/or fecal calprotectin)
4. Changes in microbiota composition (16S sequencing Illumina)
5. Normalization of colonic transit (SHAPE 0-5 markers at day 5)³⁴ among those with altered transit at baseline
6. Decrease in anxiety and/or depression scores (decrease >2 points HAD-A and/or HAD-D scores)
7. Increase in body weight and improvement in nutritional status (increased levels of micronutrients)
8. Decrease of indirect markers of mucosal integrity (IFABP2)
9. Changes in bacterial fermentation profile (SCFAs: acetate (acetic acid), propionate (propionic acid), and butyrate (butyric acid))^{26,27}.
10. Decreased number of adverse events

METHODS

Study design

Protocol date: October 2018

Randomized control trial; 3 arms of treatment: EEN plus standard or short course of CS (ECS, ECSC) vs CS alone (CS) conducted at McMaster University Medical Centre (Figure 1). The study will last 10 weeks and will involve 4 visits. At the screening visit, we will assess clinical history and symptoms, perform a physical exam and complete bloodwork after the informed consent is signed. Randomization will occur at the second visit (pre-treatment), when the inclusion and exclusion criteria and symptoms will be re-assessed, and baseline stool and urine samples will be collected. In addition, we will perform a SHAPE study and patients will be assessed by a dietitian or clinical nutrition support specialist to assess dietary factors and estimate energy needs using the Harris Benedict equation as detailed below.

Patients will be instructed to take the allocated treatment and to collect empty bottles/blisters of medication to assess the compliance at the next visit. Six weeks later (visit 3), their symptoms will be re-assessed, blood, urine and stool samples collected and SHAPE study performed. Patients will be instructed to stop the EEN or decrease the dose of CS, as detailed in the section “Follow up after treatment”. In the last visit (4th visit; 10 weeks after enrollment) we will collect information on symptoms, stool samples and urine.

The study protocol will be submitted by the investigator for approval by the Hamilton Integrated Research Ethics Board (HiREB).

Randomization process

The sequence of the treatments will be randomly generated using a computer-based pseudo-random number generator (RStudio Team (2015). RStudio: Integrated Development for R. RStudio, Inc., Boston, MA) Patients will receive one of challenges A,

B, or C consisting of CS, ECS or ECSC. A third person not involved in the study will perform the randomization to preserve treatment allocation concealed from participants and study staff. A block randomization will stratify patients by disease location (colonic/small bowel involvement). Each treatment will be assigned a number according to the randomization sequence. On recruitment, the patient will be assigned into one of three strata and given the next consecutive randomization number available for that stratum. Treatment will be not blinded for patients or study staff.

Subject recruitment

Subjects will be recruited from McMaster University Medical Centre (MUMC) Digestive Diseases Clinic, identified in an ongoing database organized in 2008 and by recruitment flyers posted at McMaster University Medical Centre, Juravinski Hospital and Hamilton General Hospital. Patients in the database signed an informed consent agreeing to be contacted for future research. Patients will be contacted by study personnel and invited to participate in the study.

After the subject has provided written consent to participate, an inclusion checklist will be completed. Subjects will be enrolled after having fulfilled all inclusion criteria, and none of the exclusion criteria.

Participants

One hundred adult patients diagnosed with IBD will be recruited at McMaster University Medical Centre. This will provide 30 subjects in each treatment arm, allowing for 10% dropout rate.

Inclusion criteria:

1. Adult patients (age 18-75 years)
2. Confirmed CD diagnosis for at least 6 months
3. Clinically active disease (CDAI >220 or HBI>6) or evidence of activity in endoscopy
4. Biochemical evidence of disease activity (CRP > 5 and/or fecal calprotectin > 250),

Exclusion criteria:

1. Current treatment with EEN
2. Intestinal obstruction, perforation, toxic megacolon, massive gastrointestinal bleeding, abdominal abscess, or other criteria considered by the investigator which preclude the use of EEN;
3. Stricture disease
4. Previous intestinal resection with a remnant bowel <180 cm
5. Treatment with prednisone in last 30 days;
6. New start or change in dose of azathioprine, 6-mercaptopurine, cyclosporine, other immunosuppressant or biologics in the last 90 days. Doses of these medications must also remain unchanged for the duration of the study.
7. New start or change in dose of 5ASA in last 30 days. 5ASA dose must remain unchanged for the duration of the study.
8. Treatment with antibiotics or probiotics use in the last 30 days.
9. Pregnancy or lactation
10. Any serious illness considered by the investigator that will interfere with the study procedure or results.

Intervention

Participants will be randomized to one of the following interventions:

1. Exclusive enteral nutrition plus corticosteroids

Patients randomized to ECS or ECSC arms will receive EEN defined as enteral feeds given exclusively as sole nutritional source over 6 weeks period in addition to the CS therapy. Hypercaloric polymeric formula (Modulen 1.5 kcal /ml; Nestle ^{22,23}) will be used for a period of 6 weeks. To increase palatability, patients will be allowed to add the “Nestle Nutrition Flavour Mix” (see Appendix). Daily volumes of formula will be prescribed based upon the patient’s estimated energy requirement (EER), calculated using the Harris Benedict equation (calculator available at <https://manytools.org/handy/bmr-calculator>), which estimates basal metabolic rate from weight and height and then applies an activity factor which ranges from 1.2 to 2.4 (Sedentary AF 1.2; mild activity 1.375, moderate activity AF 1.55, heavy activity AF 1.7, extreme AF 1.9 For details, refer to Appendix). Actual body weight or ideal body weight for height will be used in the equation depending on whether the patient is of an appropriate weight or underweight for height. Oral administration will be encouraged wherever possible, with formula volume distributed as set meals and snacks throughout the day. Nasogastric (NG) tube insertion for delivery of formula will be discussed and offered only if oral supplementation is not possible or not tolerated by the patient. Enteral feeding will be prescribed as an exclusive therapy, with exclusion of all normal diet for the period of feeding. Patients will be reviewed after 3 weeks of therapy and, when required, energy intakes will be modified by adjusting formula volumes based upon adequacy of weight changes. Volume taken per meal and distribution during the day will be recorded in the case report form. No oral foods or fluids

(except for clear liquids including water and weak tea or coffee) will be allowed during the study period. Vitamins and supplements will be allowed if doses have been stable before entering in the study, and doses are not changed during the study.

2. Corticosteroids

Patients in ECS and CS arms will receive oral prednisone 40 mg x day for 2 weeks; with subsequent taper of daily dose by 5 mg per week. Patients randomized to ECSC arm will receive oral prednisone 40 mg x day for 3 days and taper in 16 days (Figure 1). Patients randomized to the CS arm will be asked to maintain their regular diet.

Follow up after treatment

Following the completion of the period of exclusive enteral feeding, patients receiving EEN will be instructed to gradually reintroduce foods by adding one individual item every 2 days as shown in Table 1 ^{32,33} and Appendix with instructions for food introduction with coincident reduction of formula volumes under the supervision of an expert in Nutrition. The accelerated introduction of foods was based on a recent study showing similar results with additional benefits of 2 days vs 4 days ³³.

Treatment compliance

The subjects will be asked to keep the cans of Modulen and blister packs of prednisone during the entire treatment period and bring them back to the investigator at the end of that period. Compliance will be recorded in the CRF. In order to improve assessment of patient's compliance, 2 copies of a paper sheet diary will be provided at Visit 1. Patients

consuming <80% of the prescribed treatment dose throughout the study, or those who interrupted therapy for more than three consecutive days will be considered as noncompliant.

Measurements before and after treatment

- Clinical data regarding demographics, disease location and activity (Harvey-Bradshaw Index), social life and habits, past and current clinical medical background, previous surgeries, nutritional status (malnourishment, weight/ height) will be collected in CRF.
- Dietitian/ Certified nutrition support clinician: Dietary habits and caloric intake will be recorded at baseline with nutritional assessment during visits
- Bloodwork to assess for inflammatory markers, CRP, fecal calprotectin, ESR, as well as CBC, platelets, micronutrients (albumin, vitamin D, B12, A, zinc, copper, chromium)
- Questionnaires: McMaster Food frequency questionnaire(Hamilton, ON), quality of life (SIBDQOL¹³), disease activity (CDAI), anxiety and depression (HAD score, Beck inventory), and nutritional assessment (Subjective Global Assessment¹⁴ Braun Nutriscreen program)
- Gastrointestinal transit (colonic transit: SHAPE study and orocecal transit^{24,25}: patient will take one capsule and have an x ray on day five, following R.C. Evans, et al protocol, where ≥ 6 markers indicate delayed transit, therefore ≤ 5 is normalization of colonic transit).³⁴
- Stool sample (frozen samples) for microbiota composition (16S sequencing Illumina; Dr. [name]'s lab) metabolomics and metagenomics ([name]?)¹⁵

- Systemic priming to gut bacteria ([name] Lab using Flow cytometry after incubating patients' serum with cultured fecal bacteria¹⁶)
- First urine morning for metabolomics
- Intestinal permeability – indirect markers of mucosal integrity (FABP2)

Statistical analysis

There is no previous estimate on the effect of ECS compared to CS in inducing symptomatic improvement and associated changes in gut microbiota composition. Therefore, a sample size of 30 patients per arm^{28,29} should be sufficient to estimate the results and allow us to plan for future larger study. We will recruit additional 10 patients in total, to account for drop outs rates. Results will be analyzed as intention to treat (for primary outcome) and per protocol (excluding patients non-compliant with EN). The results will be expressed as n (%), mean (SD) or median (IQR) as appropriate. We will perform logistic regression to assess the association between symptomatic response and significant changes in gut microbiota composition in each group. T test or Man Whitney U test will be used as appropriate to assess differences between means. Analysis will be performed using SPSS version 21 (San Diego, CA).

Early withdrawals:

The following criteria will be considered as reasons for early discontinuation from the study (drop outs):

- Patient's decision.

- Physician's decision in case that the continuation of the patient in the study places him/her at risk.
- Patients that were not compliant with the unauthorized concomitant diets/treatments/medication will be considered as non-compliant and considered for the ITT analysis. If a subject's outcome measures worsen to the degree that they meet the study's Exclusion Criteria, study treatment will be withdrawn. Medical care will be provided as directed by the study physician and/or the subject's physician. If the required medical care conflicts with the study protocol, the subject will be placed in the intent-to-treat group. Study safety follow up will continue unless the subject withdraws, and/or is withdrawn by the study physician, and/or on the advice of the subject's physician.

Handling of adverse events

Reporting and documentation of adverse events

All adverse events occurring during the study will be reported and recorded whether or not they are considered to be non-serious, serious and/or related to the treatment. The following information will be required in each case:

- Subject and date
- Description of event
- Duration
- Frequency
- Intensity
- Seriousness
- Action taken

Protocol date: October 2018

- Outcome and sequel
- Relationship to test product

Documentation of all adverse events includes completion of the appropriate section of the case report form (AE). Documentation of a serious adverse event that requires a separate form (SAE) will be completed by the investigators in each case.

If further information or examinations are required to assess the relationship between an adverse event and treatment following the occurrence of the adverse event, all examinations or laboratory findings will be noted with their results in the CRF (section UV) or attached to a follow up file. Notification of the HiREB will also be performed in the event of an SAE during the clinical trial.

Estimated length of study: 2 yrs

REFERENCES

- 4-Ruemmele FM. Role of Diet in Inflammatory Bowel Disease. *Ann Nutr Metab*. 2016;68 Suppl 1:33-41. doi: 10.1159/000445392. Epub 2016 Jun 30
- 10-Grover Z, Burgess C, Muir R et al. Early Mucosal Healing with Exclusive Enteral

Nutrition is Associated with Improved Outcomes in Newly Diagnosed Children with Luminal Crohn's disease. *J Crohn's Colitis* 2016; 1-6

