Appendix 2-Steroids adverse events assessment (visit 2)

	Yes/no	Comments
1. Moon face		
2. Bloating		
3. Swelling		
4. Weight gain		
5. Increase appetite		
6. Hair loss		
7. Acne		
8. Stretch marks		
9. Insomnia, restlessness and or trouble sleeping		
10. Anxiety or nervousness		
11. Depression		
12. Anger/irritability		
13. Generalized weakness or fatigue		
14. Joint pain		
15. Hot flushes		
16. Visual problems (light sensitivity, decreased visual acuity)		
17. Nausea, vomiting		
18. Diarrhea		
19. Dizziness		
20. Headaches		
21. Hypertension		
22. High glucose levels		

Nestlé Nutrition Flavour Mix

Description

Nestlé Nutrition Flavour Mix is a flavouring powder formulated for use with Peptamen® Vanilla Cup and Modulen® IBD.

Presentation

60g tub (with a 0.6g scoop). Available in 5 flavours: Banana, Lemon & Lime, Chocolate, Strawberry and Coffee.

Indications

ACBS approved, prescribable on FP10 (GP10 in Scotland). For use with Vanilla flavoured Peptamen® and Modulen® IBD.

Ingredients

Banana Flavour

Dextrose, Flavouring (contains Maltodextrin), Maltodextrin, Anti-caking agent (Silicon dioxide), Colour (Curcumin), Sweetener (Sucralose).

Coffee Flavour

Dextrose, Soluble Coffee solids, Anti-caking agent (Silicon dioxide), Colour (Caramel E150c), Sweetener (Sucralose).

Strawberry Flavour

Dextrose, Flavouring (contains Maltodextrin), Acidity regulators (Lactic acid, Acetic acid), Stabiliser (Gum arabic), Preservative (Sulphur dioxide), Anti-caking agent (Silicon dioxide), Colour (Beetroot red), Sweetener (Sucralose).

Lemon & Lime Flavour

Dextrose, Flavouring (contains Maltodextrin), Modified starch, Antioxidant (E320), Citric acid, Anti-caking agent (Silicon dioxide), Colour (Curcumin), Sweetener (Sucralose).

Chocolate Flavour

Dextrose, Flavouring (contains Maltodextrin), Stabilisers (Glycerine, Gum arabic), Molasses, Anti-caking agent (Silicon dioxide), Colour (Caramel E150c), Sweetener (Sucralose).

All Flavours: Milk, Egg, Soya, Nut, Gluten and Lactose free.

Administration and dosage

Suggested intake: Add 2 scoops Nestlé Nutrition Flavour Mix per 100ml.

Shelf life and storage

Shelf life of 12 months from date of manufacture when stored at room temperature.

Contraindications

Not for intravenous use.

Not suitable for children under 3 year of age.

Precautions

To be used with caution in children between 3 and 5 years of age.

Suitable for use in children over 5 years of age.

Must be used under medical supervision.

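### Hypothesis 2 (ECSC against ECS) is not named as a contrast in any endpoint or analysis, and the only structured steroid adverse-event checklist is labelled for the visit before treatment

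*Combined protocol and SAP*

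**What the plan says.** Under Hypotheses, item 2 concerns the short-course arm: six weeks of exclusive enteral nutrition (EEN) with a short steroid course ("ECSC) will have similar efficacy than ECS and reduced number of adverse events").

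The primary endpoint is remission at six weeks for ECS compared with CS. The stem over all ten secondary endpoints reads "To determine the beneficial effect of 6 weeks of ECS as compared to CS in inducing", and item 10 beneath it is "Decreased number of adverse events". ECSC is not named in any endpoint. The general aim promises "estimated effect sizes (point estimates with confidence intervals) for all measures of interest" and names no arms. The Statistical analysis section lists two-group tests and a within-group logistic regression, again without naming a pair of arms.

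On adverse events, the protocol has a general rule that all events are recorded, and one structured 22-item form headed "Appendix 2-Steroids adverse events assessment (visit 2". Study design fixes the timing of that visit: "Randomization will occur at the second visit (pre-treatment". Its descriptions of visit 3 (week 6) and visit 4 (week 10) do not mention the form.

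**The concern.** ECSC is one of three arms, with about 30 patients, and its stated purpose is to show whether a shorter steroid course keeps the benefit with fewer adverse events. If the contrast that answers this is not named, it can still be calculated later, but not as a prespecified estimate, and the pilot exists to supply such estimates for a larger trial.

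The checklist matters for a different reason. An unnamed contrast can be repaired at analysis, but steroid-effect answers that were never collected during treatment cannot be recovered. Treatment is unblinded. General adverse-event recording does not put the same steroid questions to every arm, and the general form asks how an event relates to the test product without saying whether that means formula or prednisone.

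**Working it through.** **The plan's own figure.** 30 per arm × 3 arms = 90, and 90/(1 − 0.10) = 100. The stated total reproduces. The 30 per arm is a pilot rule with no alpha, power, effect or margin.

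**Contrasts named, place by place.**
- Hypothesis 2: ECSC against ECS, on efficacy and number of adverse events.
- Primary endpoint: ECS against CS.
- Secondary endpoints 1–10: ECS against CS.
- General aim: all measures, no arms named.
- Statistical analysis: no arms named.

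The objective in the Background also uses the label ECS for EEN with more than one steroid regimen. If ECS is read that way, the endpoints set both EEN arms against CS. That is still not ECSC against ECS.

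**Where the steroid contrast lies.** Inputs are Intervention item 2, which gives ECS and CS the same prednisone schedule, and the two tapering tables.
- ECS and CS to day 42: 7 × (40 + 40 + 35 + 30 + 25 + 20) = 7 × 190 = 1,330 mg each.
- ECSC: 3 × (40 + 30 + 20 + 10 + 5) = 3 × 105 = 315 mg, plus 5 mg for each alternate-day dose from day 16. The number of these doses is not stated; assuming 1 to 4 gives 320 to 335 mg.
- ECS minus ECSC: 1,330 − 335 = 995 mg to 1,330 − 320 = 1,010 mg. The ratio is 1,330/335 = 3.97 to 1,330/320 = 4.16.
- If ECS means both EEN arms in equal numbers, their mean is (1,330 + 320)/2 = 825 mg to (1,330 + 335)/2 = 832.5 mg, set against 1,330 mg in CS. That comparison mixes the effect of EEN with that of the shorter course.

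**Checklist timing.** Appendix 2 says visit 2. Study design makes the second visit the pre-treatment randomization visit, and exclusion criterion 5 removes patients treated with prednisone in the last 30 days. Completed as labelled, the form is filled in after 0 mg of study prednisone in every arm, so it can serve only as a baseline.

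**Precision, for illustration only.** With an assumed common remission rate p and 30 per arm, the 95% half-width for ECSC minus ECS is 1.96 × √(2p(1 − p)/30): 25.3, 24.8, 23.2 and 20.2 percentage points at p = 0.5, 0.6, 0.7 and 0.8. Any pilot of this size has such a width and the fix does not change it. It shows only why a non-significant difference would not demonstrate similarity.

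**The case against.** The strongest reply is that the general aim already covers the contrast: remission and adverse events are measures of interest in a declared three-arm pilot. This stands in part. The aim could include ECSC against ECS, but it lists measures and not comparisons, while every endpoint that does name arms names ECS and CS.

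The Statistical analysis section is equally silent on ECS against CS, so its silence is not special to Hypothesis 2. That is correct, and the weight of the point rests on the endpoint wording. Item 10 echoes the hypothesis closely, so loose drafting of the shared stem is a plausible explanation. It would still need correcting.

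On the checklist, Treatment compliance says the diary is handed out at Visit 1. If that is the visit at which treatment starts, the numbering may have slipped and visit 2 in Appendix 2 could mean week 6. The diary could equally be given at screening. Figure 1 is not reproduced and the case report form is not among the documents, so later use of the checklist cannot be excluded.

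A reader might infer three stronger things that the documents do not support:
- That adverse events go uncollected. They are recorded throughout. Weight, HAD and Beck are measured before and after treatment, and symptoms are re-assessed at visits 3 and 4.
- That item 10 is faulty because ECS and CS have the same scheduled prednisone. Equal dosing is what isolates the effect of EEN on adverse events; that comparison simply answers a different question from Hypothesis 2.
- That the trial needs a similarity margin or a powered non-inferiority test. Its aim is estimation, so it does not.

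**Conclusion.** The point holds as two wording gaps of minor to moderate importance. First, the contrast in Hypothesis 2 is not named in any endpoint or analysis, although the contrast of roughly 1,000 mg in scheduled prednisone to week 6, about fourfold, lies between ECS and ECSC. Second, the only structured steroid checklist, as labelled, collects nothing during treatment and leaves general open-label recording to carry the adverse-event half of the hypothesis.

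The milligram totals locate the contrast; they do not measure harm to the trial. They rest on the schedules as written and on the assumed one to four alternate-day doses in ECSC. The checklist conclusion rests on the visible text, with a numbering slip or an unseen later use still possible. If ECS means the ECS arm alone, the primary comparison is untouched. If it means both EEN arms, the primary contrast also changes meaning, which is why the label needs settling there too.

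**What to change.** 1. Reconcile the Appendix 2 label with the visit schedule. Administer the existing checklist in all three arms at the existing visits 3 and 4, asking about any time since the last visit, with a pre-treatment completion as baseline.
2. List ECSC minus ECS, with a 95% CI, as a secondary estimation contrast for week-6 remission and for adverse events. For adverse events, state one unit (for example, patients with at least one event) and one window. The choice of window matters because the ECS tapering table runs to week 10. Say that a non-significant difference in this pilot is not evidence of similarity.
3. State, for each endpoint including the primary, whether ECS means the ECS arm or both EEN arms.

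The cost is protocol wording and a one-page form at two existing visits, with no new visit or procedure. The downsides are a recall window of four to six weeks, answers that remain unblinded, and a more modest claim for ECSC.
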